3.2.2.3. DEFINITION OF MTD

If 2 or more patients per DL experienced a DLT, dose escalation is terminated and the MTD is the next lower DL if no more than one out of 6 patients have a DLT at that level. Once all patients enrolled in **Part A** are treated for at least 1 cycle, the study team determine the MTD to be used in **Part B** based on the safety and tolerability profile of Givinostat observed as well as the PK and PD data, if applicable.

No intra-patient dose escalation is permitted prior to determining the MTD.

At that time, patients on treatment at lower DLs can be allowed to escalate their Givinostat dose up to the MTD for the remainder part of the study (**Part A**) at the discretion of the Investigator and, after the

Document PPD

Author: PPD

Version Number:

V2.2

Version Date:

21 March 2018

Template No: CS_TP_BS016 – Revision 3

Reference: CS_WI_BS005

Effective Date: 01May2012

Copyright © 2012 Quintiles Transnational Corp. All rights reserved.

The contents of this document are confidential and proprietary to Quintiles Transnational Corp. Unauthorized use, disclosure or reproduction is strictly prohibited.

Sponsor's written authorization. Of note, patients initially dosed at lower DLs that are allowed to escalate their Givinostat dose up to the MTD for the remainder part of the study (**Part A**), are to follow the dose modification rules of **Part B** (see [paragraph 4.3.3.2](#) of the Study protocol version 3.0). Total daily dose can never exceed the MTD defined in **Part A** (i.e. 100 mg b.i.d.).

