In **Part B** patients are treated at the MTD of Givinostat established in Part A (i.e. 100 mg b.i.d., DL1).

Dose adjustments are permitted for patients who do not tolerate the protocol-specified dosing schedule, in order to allow these patients to continue the treatment with Givinostat (see [paragraph 4.3.3.1](#) and [paragraph 4.3.3.2](#) of the Study protocol version 3.0). The objective of the Givinostat dose adjustment rules described below is to optimize the response for each individual patient, avoiding specific drug-related toxicities.

Both in **Part A** and in **Part B**, patients self-administer daily Givinostat capsules at home as instructed by the Investigator (see [paragraph 4.4.7.2](#) and [paragraph 4.4.7.4](#) of the Study protocol version 3.0),

Document: PPD

Author: PPD

Version Number:

V2.2

Version Date:

21 March 2018

Template No: CS_TP_BS016 – Revision 3

Reference: CS_WI_BS005

Effective Date: 01May2012

Copyright © 2012 Quintiles Transnational Corp. All rights reserved.

The contents of this document are confidential and proprietary to Quintiles Transnational Corp. Unauthorized use, disclosure or reproduction is strictly prohibited.

except for the first drug administration (i.e. Day 1 of the Cycle 1). Patients cannot take the morning dose of Givinostat on the day selected for their timed PK and PD assessments (see [paragraph 4.5.3.2](#) and [paragraph 4.5.3.3](#) of the Study protocol version 3.0). Study drug is administered in the clinic for these specific visits, in order to obtain pre- and/or post-dose plasma levels of Givinostat. On all the other days corresponding to study visits, patients should take the morning dose of Study drug prior to the visit.

In **Part A**, the lowest dosage of Givinostat that can be dispensed to the patients is 50 mg o.d.. In this case, the patient should take the Study drug each day in the morning with fluids and between meals (i.e. to take the study drug at least 2 two hours after the last meal, or no less than 1 hour before the meal). In all other possible dosages (i.e. 50 mg b.i.d, or 100 mg b.i.d., or 150 mg/die), patients should self-administer daily Givinostat capsules at home at morning and in the evening (i.e. after 12 hours) with fluids and between meals (i.e. to take the study drug at least 2 two hours after the last meal, or no less than 1 hour before the meal).

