3.4.2. METHOD OF ASSIGNING PATIENTS TO DOSE LEVEL

When a Study site has a patient ready to enroll, prior to dosing, the site have to compile a Request for Registration Form and send it to the Sponsor or CRO team, in order to obtain the patient ID.

This request is located in a specific section of the electronic CRF, which the site should complete only after having fully compiled all the previous screening sections, including medical history, patient's characteristics, a checklist related to the inclusion and exclusion criteria to verify the eligibility of the patient, etc.

Document: PPD

Author: PPD

Version Number:

V2.2

Version Date:

21 March 2018

Template No: CS_TP_BS016 – Revision 3

Reference: CS_WI_BS005

Effective Date: 01May2012

Copyright © 2012 Quintiles Transnational Corp. All rights reserved.

The contents of this document are confidential and proprietary to Quintiles Transnational Corp. Unauthorized use, disclosure or reproduction is strictly prohibited.

The request for patient's registration contain the site ID (e.g. "IT01"), the Study part ID (i.e. "A" for **Part A** and "B" for **Part B**), the assigned patient screening number and the date of the request.

If the patient is eligible, the Sponsor or CRO confirm the enrolment of the patient assigning the related DL and the patient ID (i.e. the patient code after the enrolment confirmation) which is a combination of patient screening ID and dose level ID (e.g. "IT01-A01-DL1").

Once assigned, both the patient screening ID and the patient ID must not be reused for any other patient.

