5.1. SAFETY ANALYSIS SET (SAF)

The Safety analysis set will include all enrolled patients who receive at least one dose of study medication. All safety analyses will be conducted on this population.

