5.2. INTENT-TO-TREAT ANALYSIS SET (ITT)

The Intent-to-treat analysis set will include all recruited patients who receive at least one dose of study medication and from whom at least one post-baseline efficacy measurement is obtained.

Of note, patients who dropped the study due to drug-related TEAE(s) before that the post-baseline efficacy measurement is obtained (i.e. at C3D28 and/or at C6D28), will be considered in the ITT analysis set; in these cases, the post-baseline efficacy measurements (i.e. at C3D28 and/or at C6D28) will be considered as “No Response”, even if these assessments were not performed.

In addition, patients who have performed the visit when the post-baseline efficacy measurements (i.e. at C3D28 and/or at C6D28) had to be performed, but for which the following conditions will happen, will be excluded from the ITT analysis set:

- HCT > 45% or HCT ≤ 45% with phlebotomy(ies), AND
- at least 2 out of 4 assessments of the following will be not performed:
 - a) WBC count;

Document: PPD

Author: PPD

Version Number:

V2.2

Version Date:

21 March 2018

Template No: CS_TP_BS016 – Revision 3

Reference: CS_WI_BS005

Effective Date: 01May2012

Copyright © 2012 Quintiles Transnational Corp. All rights reserved.

The contents of this document are confidential and proprietary to Quintiles Transnational Corp. Unauthorized use, disclosure or reproduction is strictly prohibited.

- b) PLT count;
- c) Spleen evaluation by CT scan or MRI;
- d) Disease-related assessment by MPN-SAF.

This is due to the fact that is not possible to define a clinico-haematological response as per ELN response criteria in these cases.

All efficacy analyses will be conducted on this population and will be based on the *effective/actual* DL/daily doses of Givinostat at which each patient has been treated.

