 - Incidence of TEAEs leading to dose modification by primary SOC and PT.

In addition, the following primary parameter will be evaluated in **Part A** based on MTD analysis set population:

- MTD of Givinostat.

All outputs for safety outcomes will be based on the SAF analysis set, and presented by DLs (**Part A** only). There will be no planned statistical comparisons among treatment groups for safety data.

ADVERSE EVENTS

AE Investigator terms will be assigned to a PT and will be classified by primary SOC. AEs will be coded using the 20.1 version of MedDRA dictionary. TEAEs are defined as adverse events started at or after the first administration of study treatment.

See [Appendix 2](#) for handling of partial dates for AEs. In the case where it is not possible to define an AE as treatment emergent or not, the AE will be classified by the worst case (i.e. TEAE).

An overall summary of number of patients within each of the categories described in the sub-section below, will be provided as specified in the templates. Listings will include AEs and TEAEs.

A case narrative for each AE leading to treatment discontinuation (the “Action Taken with Study Drug” in section “AE” of the electronic CRF is “Definitively withdrawn”), and/or leading to death (see below), and/or ongoing at the end of treatment (the “Outcome” in the section “AE” of the electronic CRF is “Ongoing” at the time of database look) will be reported in the Clinical Study Report.

ALL TEAEs

Document PPD

Author: PPD

Version Number:

V2.2

Version Date:

21 March 2018

Template No: CS_TP_BS016 – Revision 3

Reference: CS_WI_BS005

Effective Date: 01May2012

Copyright © 2012 Quintiles Transnational Corp. All rights reserved.

The contents of this document are confidential and proprietary to Quintiles Transnational Corp. Unauthorized use, disclosure or reproduction is strictly prohibited.

Incidence of TEAEs will be presented by primary SOC and PT and also broken down further by maximum severity and relationship to Study medication.

SEVERITY AND COMMON TERMINOLOGY CRITERIA FOR ADVERSE EVENTS

AEs will be graded by the Investigators according to the Common Terminology Criteria for Adverse Events (CTCAE) version 4.03, dated 14th June 2010. The grade assigned by the Investigator will be used for this analysis.

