DLTs will be identified by using the response "Yes" at the question "Was this a Dose Limiting Toxicity Event?" on the section "AE" of the electronic CRF.

A summary of DLT by SOC and PT will be prepared.

A case narrative for each DLT will be reported in the Clinical Study Report.

SERIOUS ADVERSE EVENTS

SAEs will be identified by using the response on "Is this a serious event?" ticked as "Yes" on the "AE" section of the electronic CRF. A summary of SAE and Treatment Emergent SAEs (TESAEs) by SOC and PT will be prepared.

A case narrative for each SAE will be reported in the Clinical Study Report.

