23. DOSE MODIFICATION ANALYSIS

For patients who do not tolerate the protocol-specified dosing schedule, dose adjustments are permitted in order to allow the patients to continue the treatment with the study drug.

The objective of the Givinostat dose adjustment rules is to optimize the response for each individual patient, avoiding specific drug-related toxicities. Therefore, dose reductions or interruptions will be mandatory for specific toxicities and dose increases after an initial dose reduction will be allowed in the case of inadequate efficacy at the reduced dosage in absence of specific toxicities.

In the Cycle 1 of **Part A** dose modifications will not be allowed. Patients receiving subsequent cycles of treatment in **Part A** may have up to two dose modifications for drug related DLT's.

Each dose modification has to be recorded on the CRF and the severity of the above mentioned events will be graded according to NCI Common Terminology Criteria for AE (CTCAE v. 4.03, 14th June 2010).

Reason for treatment discontinuation and number of patients treated beyond protocol-specified discontinuation criteria will also be summarised for the safety population.

The following information will be provided for the Dosage Change, by DL (**for Part A only**) and time point:

- Number (n) and percentage (%) of patient with dose temporarily stopped; dose restarted at previous dose; dose restarted and actual dose reduced; dose reduced; dose restarted and actual dose increased;
- Listing of start/end date, type of dose change, single dose (mg) and reason for Change/Interruption.

The calculation of the compliance, in percentage and collapsed in class (Too low, Adequate, Too high), as per [Section 15.1](#) will be capture, for each patient, the deviation from the dose administration plan.

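### Part A safety tables, including the DLT summary, use the assigned dose-level label with no stated cycle limit, so events after a permitted escalation would appear in a lower-dose column

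*SAP*

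**What the plan says.** **DLT table.** SAP section 17.1 identifies DLTs by a tick box on the adverse-event form and then states: "A summary of DLT by SOC and PT will be prepared". The Cycle 1 restriction in the same section applies to escalation decisions, and section 5.4 restricts the MTD determination to Cycle 1. Neither restricts this table.

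**Grouping.** Section 17.1 adds: "All outputs for safety outcomes will be based on the SAF analysis set, and presented by DLs". Section 5.1 says of the safety set: "All safety analyses will be conducted on this population". Section 20.1 groups laboratory outputs in the same way. Section 8 takes the column labels from Table 1.1 in section 3.4.1: DL1, DL1 expanded, DL6 and DL0. Under section 3.4.2 the dose level is assigned when enrolment is confirmed and becomes part of the patient ID, which is "a combination of patient screening ID and dose level ID".

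**Dose changes.** Of Cycle 1 in Part A, section 23 says "dose modifications will not be allowed. Patients receiving subsequent cycles of treatment in" Part A may have up to two, for drug-related DLTs. In Part A, section 3.4.1 states that "the lowest dosage of Givinostat that can be dispensed to the patients is 50 mg o.d". Section 3.2.2.3 provides that, once the MTD is known, "patients on treatment at lower DLs can be allowed to escalate their Givinostat dose up to the MTD", subject to the Investigator's discretion and the Sponsor's written authorization.

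**Efficacy.** Section 5.2 bases efficacy analyses on the effective or actual "DL/daily doses of Givinostat at which each patient has been treated". Sections 5.1, 17.1 and 20 contain no such wording for safety.

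**The concern.** Safety and tolerability of the tested doses is a primary objective of Part A. A reader will take a column headed DL6 as describing 150 mg/day and one headed DL0 as describing 100 mg/day. That holds in Cycle 1. In Cycles 2 to 6 it need not hold, because the plan itself permits an escalation that leaves the label unchanged. A toxicity or platelet value arising at 100 mg b.i.d. in an escalated patient would then be read as belonging to a lower dose.

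Two further features make the DLT table harder to read. Cycle 1 DLTs, which drove the dose decision, are not separated from later ones. The two DL1 columns differ only in order of entry, so the experience at the dose taken into Part B is spread over two columns.

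**Working it through.** The plan states no figure on this point to reproduce. The check is a tracing of rules plus simple arithmetic.

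**Inputs**
- Table 1.1: DL0 is 50 mg b.i.d.; DL6 is two 50 mg capsules in the morning and one in the evening; DL1 is 100 mg b.i.d.
- Sections 3.1 and 3.2: 28-day cycles, one plus five of them.
- Section 3.4.1: Part A floor of 50 mg once daily.
- Section 3.2.2.3: ceiling of 100 mg b.i.d., the MTD.
- Section 3.7, Amendment 2 item 14: six patients at DL1 with one Cycle 1 DLT, and three patients at DL6. The DL0 number is not given.

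**Step 1: nominal daily dose by label**
- DL0: 2 × 50 = 100 mg
- DL6: 100 + 50 = 150 mg
- DL1: 2 × 100 = 200 mg

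**Step 2: change on escalation to the MTD**
- DL6: (200 − 150)/150 = 33.3%
- DL0: (200 − 100)/100 = 100%

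**Step 3: share of planned treatment in which label and dose are tied**
- Cycle 1: 28/168 = 16.7%
- Cycles 2 to 6: 140/168 = 83.3%, in which they may differ

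**Step 4: outer bounds after Cycle 1.** Permitted doses run from 50 to 200 mg/day. A DL0 event can arise at up to 200/100 = 2.0 times the labelled dose, a DL6 event at up to 200/150 = 1.33 times, and a DL1 event at as little as 50/200 = 0.25 times. The SAP does not give the reduction steps, so 50 mg/day is an outer limit.

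**Step 5: the split of DL1.** Pooled, the Cycle 1 result is 1/6 = 16.7%. If each DL1 column holds three safety-set patients, the same result appears as 1/3 = 33.3% in one and 0/3 in the other. Appendix 1 prescribes the same four labels for the MTD set, so moving to that set does not by itself pool them.

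**Step 6: does the DLT table run past Cycle 1?** No sentence says so outright. It follows from the missing limit in section 17.1, and from section 23, which foresees drug-related DLTs in later cycles as a reason for changing dose.

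**The case against.** The strongest reply is that the plan does state a rule. Sections 17.1, 8 and 3.4.2 together mean tabulation by assigned cohort, which is an accepted convention, and section 17.1 plans no statistical comparison of groups on safety. This stands: a reader might infer that the attribution rule is missing, but it can be derived from the text.

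Partial safeguards also exist. Section 17.1 requires a narrative for every DLT. Laboratory data are summarised by visit, so Cycle 1 and later platelet values are already separate. Section 23 tabulates and lists dose changes, and section 15 summarises dose intensity. With nine patients described at DL1 and DL6, individual cases can be followed. These measures let a reader reconstruct the dose at onset, but they do not change what the columns show.

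A reader might also infer from section 5.2 that an escalated patient's response is analysed at 100 mg b.i.d. while the same patient's toxicity is counted at DL6. The text does not go that far. It does not say how a patient treated at two doses is classified for efficacy, and section 8 applies the Table 1.1 labels to all statistical tables.

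Finally, the output templates are not shown and might separate cycles or doses.

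**Conclusion.** The point holds as a presentational weakness. Followed as written, the Part A safety tables can place events at 100 mg b.i.d. in the DL6 or DL0 column, mix Cycle 1 and later DLTs, and divide one dose between two columns of three. The mismatch can arise in up to 83.3% of planned treatment time and amounts to 33.3% (DL6) or 100% (DL0) of the labelled daily dose for an escalated patient.

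Its practical size is unknown. No document shows that a patient was escalated or had a DLT after Cycle 1. If neither happened, only the split of DL1 remains.

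Two stronger readings are not supported:
- **That the tables make lower doses look too toxic and 100 mg b.i.d. too safe.** Escalation acts that way, but events in DL1 patients after a dose reduction stay under DL1 and act the other way. The net direction cannot be determined.
- **That the MTD or the choice of 100 mg b.i.d. is in doubt.** The MTD rests on Cycle 1, when doses could not change. Escalation was possible only after the MTD had been set, so later events in escalated patients could not have informed it. Part B results are also untouched.

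**What to change.** In section 17.1:

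1. Tabulate Cycle 1 DLTs on the MTD set by dose, with DL1 and DL1 expanded pooled (n=6). Tabulate later-cycle DLTs separately on the safety set.
2. State that the assigned dose level is the main column for Part A safety tables. Show adverse events with onset on or after an escalation date, and laboratory visits from that date, in a separate 'escalated to 100 mg b.i.d.' column or a supplementary table, and list the dose at onset. Events after a dose reduction stay in the assigned column.
3. If no patient was escalated, replace item 2 with one sentence saying so.

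The cost is a sentence or two and at most one extra column or table, built from event onset dates and the dose-change dates that section 23 already plans to list. No new data are needed, and neither the DLT definition nor the MTD changes. The drawback is that an escalated patient appears twice, with a shorter exposure in each place, and this should be footnoted.

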17.2. PART B

The following primary efficacy parameters will be evaluated in **Part B after 3 cycles of treatment** (i.e. at the end of Cycle 3) based on ITT analysis set and PP analysis set:

- **For PV and ET (if any):** Complete response (CR) and partial response (PR) rate according to clinico-haematological ELN response criteria [1];
- **For MF (if any):** CR, major response, moderate response and minor response rate according to the EUMNET response criteria [7].

Note that only in case the enrolment in **Part A** is slow (i.e. < 5 patients enrolled in 3 months, the eligibility for this part of the study could be expanded to all patients with cMPN.

The clinico-haematological ELN response criteria [1] and EUMNET response criteria will be used to assess the preliminary efficacy of Givinostat (primary endpoint) after 3 cycles of treatment in **Part B** for PV/ET and MF patients, respectively.

In all cases, the medical judgment of the Investigator's is taken into account. In particular, if the Investigator's clinical response assessment – that takes into account the overall medical judgment of the

Document: PPD

Author: PPD

Version Number:

V2.2

Version Date:

21 March 2018

Template No: CS_TP_BS016 – Revision 3

Reference: CS_WI_BS005

Effective Date: 01May2012

Copyright © 2012 Quintiles Transnational Corp. All rights reserved.

The contents of this document are confidential and proprietary to Quintiles Transnational Corp. Unauthorized use, disclosure or reproduction is strictly prohibited.

specific patient's case - is not in agreement with the exact application of the clinico-haematological ELN or EUMNET response criteria, the Investigator's assessment will supersede the "mathematical" application of these criteria and used for analysis into study report. Also mathematical application of ELN response criteria (not agreed by the medical site team) will be analyzed.

Frequency and percentage of patients in each response category (CR, PR, no response (NR) for PV and ET; CR, major response, moderate response, minor response and NR rate for MF) will be presented at Cycle 3 Day 28 (C3D28). Of note, patients who dropped the study due to drug-related TEAE(s) before that the post-baseline efficacy measurement is obtained (i.e. at C3D28 and/or at C6D28), the post-baseline efficacy measurements (i.e. at C3D28 and/or at C6D28) will be considered as "No Response*", even if these assessments were not performed. "*" will allow to distinguish them from them from the therapeutic response evaluation result of "No Response", that will be reported without "*" (i.e. "No Response"). Other missing data will not be replaced, if not otherwise specified.

For **Part B** – Stage 1, Simon's design hypothesis will be evaluated by calculating the frequency and 95% CI of patients with a CR and/or PR at C3D28.

For Part B – Stage 2, the efficacy of Givinostat will be evaluated by means of a generalized linear model (logit link function and binomial distribution) adjusting for age, sex and disease type (PV, ET, MF). The therapeutic response will be collapsed in two categories in order to improve the model performance:

- For PV and ET:
 - a) "Responders" (i.e. CR and PR), and
 - b) "Not Responders" (i.e. NR);
- For MF:
 - a) "Responders" (i.e. CR, major response, moderate response and minor response), and
 - b) "Not Responders" (i.e. NR for MF).

In addition, the following primary safety parameters will be evaluated in **Part B after 3 cycles of treatment** (i.e. at the end of Cycles 3, or including data related to Cycles 1, 2 and 3) based on SAF analysis set:

- Number of patients experiencing AEs.
- Type, incidence, and severity of treatment-related AEs, graded according to CTCAE v. 4.03 (14th June 2010).

AEs will be coded using MedDRA dictionary (using the 20.1 version). AEs will be reported on a per patient basis. If a patient has more than one AE for a treatment that is coded to the same PT, the patient will be counted only once for that PT. Similarly, if a patient has more than one AE for a treatment within a SOC category, the patient will be counted only once in that SOC category. A patient with multiple CTCAE grades for an AE will be summarised under the maximum CTCAE grade recorded for the event.

Document: PPD

Author: PPD

Version Number:

V2.2

Version Date:

21 March 2018

Template No: CS_TP_BS016 – Revision 3

Reference: CS_WI_BS005

Effective Date: 01May2012

Copyright © 2012 Quintiles Transnational Corp. All rights reserved.

The contents of this document are confidential and proprietary to Quintiles Transnational Corp. Unauthorized use, disclosure or reproduction is strictly prohibited.

Any AE which started at or after the first administration of Study treatment will be considered a TEAE. If the start date is missing for an AE, the AE will be considered to be treatment emergent.

An overview of AEs including the number of patients with at least one AE, at least one TEAE, at least one drug-related TEAE, at least one TESA, any SAE, any AE leading to death, any TEAE leading to death, any TEAE leading to drug discontinuation, at least one grade ≥ 3 TEAE, will be presented. The following AE frequency tables will be also provided:

- Incidence of TEAEs by primary SOC and PT;
- Incidence of drug-related TEAEs by primary SOC and PT;
- Incidence of TEAEs by maximum severity, primary SOC and PT;
- Incidence of TEAEs by strongest relationship, maximum severity, primary SOC and PT;
- Incidence of TESAEs by primary SOC and PT;
- Incidence of TEAEs leading to study drug discontinuation by primary SOC and PT;
- Incidence of TEAEs leading to dose modification by primary SOC and PT.

The primary safety parameters will be evaluated in **Part B after 3 cycles of treatment** (i.e. at the end of Cycles 3, or including data related to Cycles 1, 2 and 3) based on SAF analysis set and taking into account the same rules describes in the paragraphs [17.1](#).

